#### **5.2.1.5. Subgroup Analysis**

Analysis of the primary endpoint as discussed in section 5.1 will also be performed for the subgroups defined in section 2.4.

#### **5.2.1.6. Repeated Measures Analysis**

The primary endpoint will also be analyzed using a generalized estimating equation (GEE) using results from all post-dose timepoints (0.5, 1, 2 and 24 hours). The model will include treatment, period, sequence, weight group (at randomization), predose (immediately prior to study drug administration) headache pain intensity, timepoint as time factor and treatment by timepoint interaction. The logit link function will be used with an unstructured within subject covariance matrix. Odds ratio, p-value for the treatment effect and the corresponding 95% confidence interval will be presented for each timepoint. If the model fails to converge due to the unstructured covariance matrix, a simpler covariance matrix will be employed in the order of 1) autoregressive (1) [SAS PROC GEE type = AR(1)], 2) exchangeable [type = EXCH]. The first covariance structure that does not have a convergence problem will be the one used for the analysis.

### **5.3. Secondary Efficacy Endpoints in Part 1**

Secondary efficacy endpoints include the following:

- Proportion of subjects with pain-free status 2-hour postdose for low dose group
- Proportion of subjects with pain-free status at 30 minutes, 1-hour, and 24-hour postdose (will also be performed for the subgroups defined in section 2.4 for the high dose group)
- Proportion of subjects without photophobia at 30 minutes, 1-hour, 2-hour, and 24-hour postdose
- Proportion of subjects without phonophobia at 30 minutes, 1-hour, 2-hour, and 24-hour postdose
- Proportion of subjects without nausea at 30 minutes, 1-hour, 2-hour, and 24-hour postdose
- Proportion of subjects with a headache response (defined as a reduction in headache severity from moderate (2) or severe (3) to mild (1) or none (0)) at 30 minutes, 1-hour, 2-hour, and 24-hour postdose (will also be performed for the subgroups defined in section 2.4 for the high dose group)

- Proportion of subjects who use rescue medication within 2, 3, 4 and up to 24 hours postdose. Note: if subject diary includes records of rescue medication that started prior to the start of migraine, such medications will be ignored as incorrect diary entry. If rescue medications are recorded with missing start date/time, worse case will be assumed, i.e. that the rescue medication was taken at the same time as the migraine started.
- Proportion of subjects with headache recurrence during 2 to 24 hours postdose for the subset of subjects who attained a 2-hour pain-free response
- Proportion of subjects with headache recurrence (with headache severity higher than that at 2 hours) during 2 to 24 hours postdose for the subset of subjects who attained a 2-hour headache response
- Proportion of subjects with sustained headache response 2 to 24 hours postdose defined as the proportion of subjects who attained a 2-hour headache response and who did not experience a headache recurrence (pain intensity moderate or severe) between 2 and 24 hours
- Proportion of subjects with sustained pain free response 2 to 24 hours postdose defined as the proportion of subjects who attained a 2-hour pain free response and who remained pain free between 2 and 24 hours
- Time to rescue medication. For those subjects who did not use rescue medication, the time to rescue medication is censored at 24 hours after dosing. Additionally, descriptive summary of time to rescue medication will be presented for those subjects who did take a rescue medication. Note: if subject diary includes records of rescue medication that started prior to the start of migraine, such medications will be ignored as incorrect diary entry. If rescue medications are recorded with missing start date/time, time to rescue medication will be imputed as zero.

For all proportion endpoints, a GEE model similar to the primary analysis will be conducted for the low dose group and high dose group separately.

For the time to use of rescue medication, a Cox proportional hazards model for crossover data ([France et al 1991](#)) with treatment, period, weight, and baseline headache pain intensity will be used.

Time to use of rescue medication will also be presented graphically using the Kaplan-Meier estimates.

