## 1.2. Sample Size and Power

Part I of this study is a randomized, double-blind, placebo-controlled, 2-period, crossover outpatient study with a 6-week placebo run-in period.

Approximately 426 subjects will be enrolled to the placebo run-in period to randomize 288. With the 5:1 (high dose:low dose) randomization ratio for each of the two weight strata, it is estimated that 240 subjects will be randomized in the high-dose group and 48 subjects will be randomized to the lower dose level.

The sample size is based on detecting a difference in the percentage of subjects treated with a high dose (2.5 mg in the <50 kg weight stratum and 5 mg in the ≥50 kg weight stratum) who are pain free at 2 hours between ZNS and placebo. In this crossover trial, 240 high-dose-treated subjects will be adequate to detect a clinically relevant difference of 0.11 in the percentage of subjects who are pain free at 2 hours between ZNS and placebo as statistically significant (0.05, two tailed) with 90% power assuming a standard deviation of 0.5.

Approximately 48 subjects will be randomized in the low dose level (1 mg in the <50 kg weight stratum and 2.5 mg in the ≥50 kg weight stratum). The data from the low dose level will be summarized to explore dose-response relationship.

Based on other migraine crossover studies, dropout rates during the placebo run-in period ranged from 12% to 50%. Based on this, approximately 426 subjects will be enrolled into the placebo run-in period to randomize 288. This allows for approximately 32% dropout during placebo run-in period.

Approximately 100 subjects who complete the double-blind crossover phase will enter the 6-month OLE to enable at least 50 subjects to complete at least 6 months treating on average at least one migraine attack per month (treating up to 4 migraine attacks per month) with ZNS. Part II of the study is an OLE with subjects who successfully complete Part I of the study.

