## **2. GENERAL CONSIDERATIONS FOR DATA ANALYSIS**

Part 1 and 2 of the study will be analyzed separately. Separate sets of tables, listings and figures will be prepared for Part 1 and Part 2.

After all subjects have completed the double-blind phase of the study (Part I) or prematurely discontinued from the study, all data in Part I will be cleaned, the database will be frozen (soft lock), the study will be unblinded, and an analysis of Part I (double-blind) data will be performed. This will be the primary analysis of the study and a type I error rate (5%) will be allocated for this analysis.

All statistical tests will be 2-sided and performed at the 5% significance level, without multiplicity adjustment.

Likewise, after all subjects have completed Part II (OLE) of the study or prematurely discontinued from the study, all outstanding data queries have been resolved or adjudicated as unresolvable, and the data have been cleaned and finalized, the final analysis of the data will be performed. This final analysis will mainly focus on the OLE.

Analysis results will be presented using descriptive statistics. For categorical variables, the number and percentage of subjects in each category will be presented; for continuous variables, descriptive statistics (the number of subjects [n], mean, standard deviation [SD], median, minimum, and maximum) will be presented.

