## **5. EFFICACY ANALYSES**

### **5.1. Primary Efficacy Endpoint in Part 1**

A patient diary is used to collect the patients' self-assessment of headache pain intensity. Pain intensity is rated on a 4-point scale: severe (3), moderate (2), mild (1), and none (0).

The primary efficacy endpoint is the proportion of subjects with pain-free status at the 2-hour time point for the high dose group during the double-blind phase of the study. Pain-free status is defined as a reduction in the headache pain intensity rating from moderate (2) or severe (3) pain at predose to none (0) at 2-hour post dose, without using rescue medication and without napping/sleeping prior to the 2-hour assessment.

For the primary efficacy endpoint analysis, all high-dose subjects in the FAS are included.

The primary endpoint will be analyzed using a generalized estimating equation (GEE). The model includes treatment, period, sequence, weight group (at randomization), and predose (immediately prior to study drug administration) headache pain intensity. The logit link function is used with an unstructured within subject covariance matrix. Odds ratio, p-value for the treatment effect and the corresponding 95% confidence interval will be presented.

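### Section 5.3 tests two recurrence endpoints only among 2-hour responders, so their GEE p-values are not valid tests of a drug effect on recurrence

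*SAP*

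**What the plan says.** SAP section 5.3 defines two recurrence endpoints on restricted denominators. One is the "Proportion of subjects with headache recurrence during 2 to 24 hours postdose for the subset of subjects who attained a 2-hour pain-free response". The other counts recurrence "during 2 to 24 hours postdose for the subset of subjects who attained a 2-hour headache response".

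The same section then states: "For all proportion endpoints, a GEE model similar to the primary analysis will be conducted for the low dose group and high dose group separately". Section 5.1 gives that model: "The model includes treatment, period, sequence, weight group (at randomization), and predose (immediately prior to study drug administration) headache pain intensity", and "The logit link function is used with an unstructured within subject covariance matrix". Section 2 adds: "All statistical tests will be 2-sided and performed at the 5% significance level, without multiplicity adjustment". The two recurrence endpoints are not exempted, and there is no caveat about how their subsets arise.

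On group sizes, section 1.2 says "it is estimated that 240 subjects will be randomized in the high-dose group and 48 subjects will be randomized to the lower dose level". The only convergence rule is in section 5.2.1.6, for the repeated-measures analysis: "If the model fails to converge due to the unstructured covariance matrix, a simpler covariance matrix will be employed".

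Section 5.3 also lists sustained headache response and sustained pain-free response from 2 to 24 hours. Neither is restricted to responders.

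**The concern.** Randomisation makes all ZNS-treated attacks comparable with all placebo-treated attacks. It does not do so for the attacks that responded. If ZNS works, its responder set contains attacks that placebo would not have resolved. If those attacks are more prone to return, ZNS responders show more recurrence even though the drug does nothing to recurrence. Adjusting for predose severity does not remove this, because difficulty is only partly captured by a two-level severity rating. The crossover pairing also weakens, since a child who responds in one period only contributes a single record.

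At stake is a significant finding of more recurrence on ZNS that reflects selection. The distortion grows with 2-hour efficacy. In the low-dose group the same model is asked of very few attacks.

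**Working it through.** **The plan's own figures.** Section 1.2 gives a difference of 0.11, SD 0.5, two-sided 0.05 and 90% power. The paired formula is n = ((1.960 + 1.282) × 0.5 / 0.11)² = 217.1, so 218. The planned 240 gives about 92.6% power, so it is conservative; this does not bear on the point. The split reproduces: 288 × 5/6 = 240 and 288 × 1/6 = 48.

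**Inputs not in the SAP (assumed).** The SAP gives no 2-hour response rate, no recurrence rate and no link between attack difficulty and recurrence.

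**How selection alone shifts the rate.** Assume pain-free 30% on ZNS and 19% on placebo (difference 0.11), and recurrence of 20% in attacks that placebo would also resolve, whichever treatment is given.
- Placebo responders: 20% recur, odds 0.25.
- Extra ZNS responders recur at 40%: (19 × 0.20 + 11 × 0.40) / 30 = 8.2/30 = 27.3%. Odds ratio (8.2/21.8) / 0.25 = 1.50.
- Extra ZNS responders recur at 50%: (3.8 + 5.5) / 30 = 31.0%. Odds ratio (9.3/20.7) / 0.25 = 1.80.
- Extra ZNS responders recur at 20%: both arms 20%, odds ratio 1.

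**High dose, simulated test size (no drug effect on recurrence).** 500 trials of 240 children per scenario; logit GEE with the section 5.1 covariates, independence working correlation, robust SE; within-child share of latent difficulty 0.5.

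| Assumed 2-hour response, ZNS vs placebo | Recurrence in extra responders (others 20%) | Rejection at 5% |
|---|---|---|
| Pain-free 30% vs 19% | 20% / 40% / 50% | 4% / 15% / 26% |
| Headache response 55% vs 40% | 20% / 30% / 40% / 50% | 5% / 8% / 16% / 30% |

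A separate run under the same null gave 4.5% at equal risk and 14% to 28% when the extra responders recur 2 to 2.5 times as often.

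A second model let recurrence rise smoothly with difficulty, with b the log-odds per SD, and used one estimated within-subject correlation as section 5.1 implies. It used 1,500 trials per scenario and placebo response of 10% to 45%.

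| ZNS effect on 2-hour response | b=0 | b=1 | b=2 | b=3 |
|---|---|---|---|---|
| +11 points | 3–5% | 6–10% | 20–24% | 37–42% |
| +20 to 25 points | not run | 18–26% | 55–71% | 83–92% |

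With no ZNS effect on 2-hour response, rejection was 5% to 6% even at b = 2 to 3. Nearly all excess rejections at +11 points showed ZNS worse. At 26% vs 15% the spurious median odds ratio was 1.4, 1.8 and 2.4 for b = 1, 2 and 3.

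**Loss of pairing.** In one high-dose scenario (26% vs 15%, b = 0.5, within-subject latent correlation 0.2) there were on average 98 responder records and 13.2 children responding in both periods. So 98 − 2 × 13.2 = 71.6 records (73%) came from children with a single responding attack.

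**Low dose (n=48), assuming the same 11-point difference.** The GEE has 6 parameters: intercept, treatment, period, sequence, weight group and predose severity.
- Pain-free recurrence, placebo pain-free 10% to 20%: 48 × (0.10 + 0.21) = 14.9 to 48 × (0.20 + 0.31) = 24.5 attacks, with 2 to 9 recurrences and 1.5 to 3.9 children responding twice. Separation in 54% to 99% of trials; usable fit in 1% to 40%.
- Headache-response recurrence, 56% vs 45%: separation in 6% to 72%; usable fit in 26% to 93%, and 55% to 93% once recurrence is 25% or more. At 41% vs 30%: usable fit in 12% to 69%.

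The fallback in section 5.2.1.6 does not cover these models. It changes only the covariance structure, which cannot cure separation.

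**The case against.** The strongest reply has four parts.

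1. **Size is assumed.** The SAP supplies only the 0.11 difference, and the inflation disappears if the extra responders recur like the others. This stands: the figures are a range under stated assumptions. It does not rescue the test, whose validity would depend on an untestable equality.
2. **No recurrence hypothesis is stated.** The SAP names a proportion in a subset, and the model compares that proportion. As description this is fair. But a treatment odds ratio and p-value beside randomised comparisons will be read as a treatment effect.
3. **Separation is not the same as an inestimable treatment effect.** Much of it lies in weight group or predose severity, where software may still print a treatment estimate. For low-dose pain-free recurrence, an arm with none or all recurring occurred in 3% to 59% of trials. This stands. Section 1.2 also says the low-dose data are for exploring dose-response, which lowers the stakes and favours description.
4. **The sustained endpoints are already listed and do not test recurrence.** This stands. They combine 2-hour efficacy with durability. With no drug effect on recurrence but ZNS effective at 2 hours, a paired z-test (4,000 trials, n=240, first-table scenarios) rejected in 79%, 56% and 44% for sustained pain-free, and in 87%, 77%, 65% and 49% for sustained headache response. Another run under that null gave 42% to 77%. They validly compare benefit held to 24 hours; they cannot stand in as a test of durability alone.

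**Conclusion.** The point holds in a limited form. The GEE p-values for the two responder-only recurrence endpoints are not valid tests of a drug effect on recurrence, because the subset is selected by a treatment-affected outcome. At the planned 11-point pain-free difference, the chance of a spurious result is near 5% with equal recurrence risk and roughly 14% to 26% when the extra responders recur 2 to 2.5 times as often. A steeper assumed link or a larger 2-hour effect raises it further.

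Three stronger readings are tempting and not supported:
- That the test will reject. At the planned effect it rejects in a minority of trials in every scenario examined.
- That the low-dose models generally cannot be fitted. Separation is usual for pain-free recurrence at placebo pain-free rates of 10% to 20%; the headache-response version often fits.
- That the trial's main result is in doubt. These are secondary endpoints, and the primary analysis uses all high-dose FAS subjects.

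**What to change.** In section 5.3:
- Exempt the two responder-only recurrence endpoints from the GEE and its p-value. Report n/N and percent by treatment for the high- and low-dose groups, with a statement that this is not a randomised comparison.
- Keep sustained headache response and sustained pain-free response as the randomised comparison of benefit held to 24 hours. State that the denominator is all treated attacks in the FAS and that 2-hour non-responders count as not sustained. This also stops the observed-cases rule for 24 hours in section 2.5.1.1 from dropping known failures.
- State that these endpoints combine 2-hour efficacy with durability and do not test recurrence alone.
- Read low-dose results as descriptive.

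In the high-dose group the sustained pain-free GEE in all FAS subjects fitted in at least 99.9% of simulated trials and rejected in 4.5% to 5.5% when ZNS had no effect at all. In the low-dose group it fitted in only 58%, 79% and 88% at placebo pain-free rates of 10%, 15% and 20%, hence the last item.

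The cost is SAP wording, with no new data. The downside is that there will be no p-value for recurrence among responders.

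### SAP section 5.3 gives headache recurrence inconsistent thresholds, so a none-to-mild attack counts as both a recurrence and a sustained response, and it tests recurrence in subsets selected by response

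*SAP*

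**What the plan says.** SAP section 5.3 uses the term headache recurrence in three secondary endpoints.

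- For 2-hour pain-free subjects: "Proportion of subjects with headache recurrence during 2 to 24 hours postdose for the subset of subjects who attained a 2-hour pain-free response". No severity threshold is given.
- For 2-hour headache responders (mild or none at 2 hours): "Proportion of subjects with headache recurrence (with headache severity higher than that at 2 hours) during 2 to 24 hours postdose". The threshold is relative to the child's own 2-hour rating.
- Within sustained headache response, which starts from the same headache responders, success belongs to those "who did not experience a headache recurrence (pain intensity moderate or severe) between 2 and 24 hours". This threshold is absolute.

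Sustained pain-free response is worded without the term: it requires subjects "who attained a 2-hour pain free response and who remained pain free between 2 and 24 hours".

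On analysis, section 5.3 adds: "For all proportion endpoints, a GEE model similar to the primary analysis will be conducted", for the low-dose and high-dose groups separately. Section 2 sets every test at a two-sided 5% level without multiplicity adjustment. Section 2.5.1.1, item 5, leaves the 24-hour rating unimputed. Section 5.5, on changes from the protocol-specified efficacy analyses, does not mention recurrence.

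**The concern.** A reader of the study report will expect recurrence and sustained response, both starting from the same 2-hour headache responders, to add to 100% among those with a 24-hour rating. Under these definitions they do not.

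The any-rise rule also has a floor problem. A child at none at 2 hours and mild at 24 hours has recurred. A child who was mild at both times has not, although both end in the same state and the first had the better 2-hour result. Because only attacks at none at 2 hours can be caught this way, the rule does not fall evenly on two treatments whose responders differ in how many are pain-free.

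Separately, both recurrence endpoints are modelled in subsets defined by response to the treatment being compared. At stake are the secondary results on durability of effect. The 2-hour primary endpoint is not involved.

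**Working it through.** **1. Enumerate the cases.** Inputs: the four-point scale (section 5.1), entry at mild or none at 2 hours (section 5.3), and 24 hours as the only scheduled rating after 2 hours (section 1.1). That gives 2 × 4 = 8 pairs.

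| 2 h | 24 h | Recurrence, any rise | Recurrence, moderate or severe | Sustained headache response |
|---|---|---|---|---|
| none | none | no | no | yes |
| none | mild | **yes** | **no** | **yes** |
| none | moderate | yes | yes | no |
| none | severe | yes | yes | no |
| mild | none | no | no | yes |
| mild | mild | no | no | yes |
| mild | moderate | yes | yes | no |
| mild | severe | yes | yes | no |

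Seven pairs agree. One, none to mild, is both a recurrence and a sustained response.

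**2. Size of the difference between the rules.** For one treatment's 2-hour responders, let f be the share at none, a = P(none to mild), s0 = P(none to moderate or severe) and s1 = P(mild to moderate or severe).

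- Any rise: f(a + s0) + (1 − f)s1
- Moderate or severe: f·s0 + (1 − f)s1
- Difference: f·a

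The SAP gives none of these rates, so everything numerical below is assumed. Take f = 0.6 for treatment A and 0.4 for treatment B, with the same a in both. The A-minus-B comparison then moves by (0.6 − 0.4)·a against A:

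| a | Shift against A |
|---|---|
| 0.05 | 1 point |
| 0.10 | 2 points |
| 0.20 | 4 points |
| 0.30 | 6 points |

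**3. What the report would show.** With a = 0.20, s0 = 0.10, s1 = 0.20 and 100 responders per treatment:

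- A, any rise: 60 × 0.30 + 40 × 0.20 = 26 recurrences. Moderate or severe: 60 × 0.10 + 40 × 0.20 = 14, so 86 sustained. Reported total: 26 + 86 = 112.
- B, any rise: 40 × 0.30 + 60 × 0.20 = 24. Moderate or severe: 40 × 0.10 + 60 × 0.20 = 16, so 84 sustained. Reported total: 24 + 84 = 108.

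A has more recurrence than B (26 v 24) and also more sustained response (86 v 84). With the moderate-or-severe rule in both endpoints, each treatment totals 100.

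**4. When the sign changes.** With equal transition rates, A minus B is (fA − fB)(a + s0 − s1) under any rise and (fA − fB)(s0 − s1) under moderate or severe.

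- a = 0.20, s0 = 0.10, s1 = 0.20: +2 points against −2, a reversal.
- a = 0.10, s0 = 0.10, s1 = 0.30: −2 points against −4, no reversal.

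If a differs between treatments, the shift is fA·aA − fB·aB. It is zero when aA/aB = fB/fA = 0.4/0.6 = 0.67, and it favours A below that ratio.

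**5. The subset models.** Entry to either recurrence subset depends on the 2-hour outcome of the attack. A child who responds on only one treatment contributes only that attack, so for that child the within-subject comparison is lost. The remaining attacks are selected differently on the two treatments, and the contrast is no longer a randomised one.

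**The case against.** Each of the two headache-responder endpoints carries its own rule in parentheses, so a programmer would compute each in one way only. On this view they are two legitimate quantities, worsening after 2 hours and loss of headache response, that share a label, and they differ in one cell of eight. This stands: neither of those two endpoints is uncomputable. It does not remove the contradiction, because the sustained endpoint is defined as the absence of recurrence. Nor does it help the pain-free subset, where there is no rule and the programmer must choose.

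A reader might go further and infer that the any-rise rule penalises ZNS, or that the report will show more recurrence on ZNS. The SAP does not support that. It gives no transition rates; the shift needs none-to-mild return to be reasonably similar on the two treatments; and the final sign also depends on how often mild attacks worsen. A higher pain-free rate over all attacks, which is what the primary endpoint tests, also does not by itself guarantee a higher pain-free share among responders.

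Two further objections are fair. Selection by response affects any responder-subset endpoint, and the SAP already lists the sustained endpoints, with efficacy placed on the FAS in section 2.1.2. But section 5.3 still sends the subset rates to GEE. And moving inference to the whole FAS does not fit with observed cases only at 24 hours unless a missing-data rule is added; the fix must include one.

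**Conclusion.** The inconsistency is established from section 5.3 alone: two thresholds for one term in the same responders, and no threshold in the pain-free subset. One of eight rating pairs is counted on both sides, so recurrence and sustained headache response are not complements.

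The any-rise rule adds exactly f·a to each treatment's recurrence rate. The comparison therefore shifts against the treatment whose responders include more pain-free attacks, unless none-to-mild return is sufficiently rarer there. The 1-to-6-point range rests wholly on assumed shares and rates, and the shift need not reverse the comparison.

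That the subset GEE tests are not randomised comparisons holds whatever the rates are. The consequence is confined to secondary endpoints, but the correction is cheap and worth making.

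**What to change.** Before unblinding, amend section 5.3 as follows.

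1. In the 2-hour headache-response subset, define recurrence as return to moderate or severe pain, the threshold the SAP already uses for sustained headache response. If any rise is still of interest, report it under another name, such as worsening after 2 hours.
2. In the 2-hour pain-free subset, define recurrence as any return of pain, the complement of sustained pain-free response. A none-to-mild attack will still be a recurrence in this subset and a sustained headache response in the other, so each label should name its subset.
3. Report both subset recurrence rates descriptively, without GEE p-values.
4. Base between-treatment inference on the two sustained endpoints with all FAS attacks in the denominator and 2-hour non-responders counted as failures. State how responders with a missing 24-hour rating are counted, and align section 2.5.1.1, item 5, with that rule.

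Cost: SAP wording, one missing-data decision and two fewer model p-values. No new data are needed, and the primary endpoint is unaffected.

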Eligible placebo non-responders will be randomized to one of two treatment sequences within their respective body weight stratum determined immediately prior to randomization: ZNS followed by placebo or placebo followed by ZNS ([Table 1](#)). Subjects weighing less than 50 kg will be allocated randomly to receive ZNS 2.5 mg or 1 mg in a 5:1 fashion during the ZNS treatment. Subjects weighing at least 50 kg will be allocated randomly to receive ZNS 5 mg or 2.5 mg in a 5:1 fashion during the ZNS treatment ([Table 2](#)). Following randomization, subjects will have up to 6 weeks to treat a migraine attack of moderate or severe intensity. During each treatment period, subjects will treat a single moderate to severe migraine attack with study drug within approximately 20 minutes of the headache pain reaching moderate or severe intensity. Headaches occurring while the child is at school will not be treated with study drug. Headache pain intensity will be assessed by the subjects immediately prior to treatment with study drug and at 30 minutes, 1, 2, and 24 hours postdose using a subject diary containing the 4-point headache pain intensity scale. Associated migraine symptoms will also be assessed at these time points. Subjects who do not obtain satisfactory relief of migraine pain by 2 hours after taking study drug will be permitted to treat with their protocol-allowed pre-study acute migraine medication (eg,

nonsteroidal anti-inflammatory drugs [NSAIDs] or acetaminophen) at that time or at any time thereafter, if the headache does not resolve or if it recurs, with the exception that all triptans and ergot derivatives are prohibited for 24 hours following the dose of study treatment. After treating a migraine attack in the first treatment period, the subject will return to the study site to receive study drug for the second treatment period. Subjects will then have up to 6 weeks to treat a second migraine attack of moderate or severe intensity.

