## 8. CODE SAMPLES

### 8.1. Primary analysis GEE model

```
proc genmod data=...;
  class trtp aperiod trtseqp usubjid weightcat base;
  model avalc(event='Y') = trtp aperiod trtseqp weightcat base / dist=binomial
link=logit type3;
  repeated subject=usubjid(trtseqp) / type=UN within=aperiod;
  lsmeans trtp / diff cl oddsratio ilink;
run;
```

The input dataset needs to include a record per each subject/treatment period. Explanation of variables:

1. TRTP: planned treatment at the time of assessment
2. APERIOD: treatment period number (1 or 2)
3. TRTSEQP: planned sequence of treatments (ZNS-Placebo or Placebo-ZNS)
4. USUBJID: unique subject identifier
5. WEIGHTCAT: weight category (<50 kg or >=50 kg)
6. BASE: pre-dose headache severity
7. AVALC: response variable (Y = response achieved, N = not achieved).

Odds ratios, their confidence intervals and p-values will be found in the Diff's ODS dataset.

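### The photophobia, phonophobia and nausea analyses leave out predose status of the same symptom, which gives up a little precision and shrinks the all-attack difference

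*SAP*

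**What the plan says.** SAP Section 5.3 lists three associated-symptom endpoints. The first reads "Proportion of subjects without photophobia at 30 minutes, 1-hour, 2-hour, and 24-hour postdose"; phonophobia and nausea are worded the same way. None requires the symptom to be present before dosing. Section 2.1.2 places all efficacy analyses in the full analysis set, so every treated attack counts.

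For the model, Section 5.3 states "For all proportion endpoints, a GEE model similar to the primary analysis will be conducted", separately for the high-dose and low-dose groups. The primary model (Section 5.1) has treatment, period, sequence, weight group and predose pain intensity. The code in Section 8.1 confirms the one baseline term: "BASE: pre-dose headache severity".

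The predose symptom data exist. Section 1.1 lists the diary times for pain, starting just before dosing, and adds "Associated migraine symptoms will also be assessed at these time points". Section 4.3 tabulates nausea and light and sound sensitivity as yes/no features of a child's usual migraine, so the plan does not assume that every child has them.

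The SAP nowhere adds predose symptom status to a model, limits an analysis to attacks with the symptom, or plans a sensitivity analysis of that kind.

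**The concern.** The pain endpoints are defined as a change from a moderate or severe predose state and are adjusted for predose pain. The symptom endpoints have neither feature for their own baseline: they are adjusted for the baseline of a different variable. A child with no nausea at dosing and none at 2 hours is a nausea success on either treatment.

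Two things are at stake, both modest. First, a baseline value that plausibly predicts the outcome, and is already collected, is left out of the model, so the treatment comparison is less precise than it could be. Second, the reported all-attack difference mixes attacks in which the symptom could be relieved with attacks in which there was nothing to relieve, which makes the tabulated effect smaller and harder to interpret.

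**Working it through.** **The plan's own figure.** The only sizing in the SAP is for 2-hour pain freedom: "240 high-dose-treated subjects will be adequate to detect a clinically relevant difference of 0.11", "as statistically significant (0.05, two tailed) with 90% power assuming a standard deviation of 0.5". Taking 0.5 as the SD of the within-child difference:

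n = (0.5 × (1.960 + 1.282) / 0.11)² = 217.1, so 218.

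At 240, power = Φ(0.11 / (0.5/√240) − 1.960) = 92.6%. So 240 is adequate and slightly conservative. No power figure is given for the symptom endpoints. The number carried forward is 240 pairs in the high-dose group.

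**Shrinkage of the all-attack difference.** Let q be the share of attacks with the symptom at dosing. Assume that attacks without it have the same symptom-free rate on both treatments. Then

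all-attack difference = q × (difference in symptomatic attacks).

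Assumed rates (none is in the SAP): 92% symptom-free at 2 hours if absent predose; 55% on ZNS and 42% on placebo if present.

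| q | ZNS | Placebo | Difference |
|---|---|---|---|
| 0.40 | 0.40×55 + 0.60×92 = 77.2% | 0.40×42 + 0.60×92 = 72.0% | 5.2 points |
| 0.60 | 69.8% | 62.0% | 7.8 points |
| 0.75 | 64.25% | 54.5% | 9.75 points |
| 1.00 | 55% | 42% | 13 points |

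**Power with and without the covariate.** On these rates, with 240 pairs, 1,500 simulated trials per setting, an independence GEE and predose pain in both models, adding predose symptom status changed power as follows:
- within-child latent correlation of predose symptoms from 0 to 0.8: gain of about 2 to 7 points;
- correlation 0.95: gain of about 1 point;
- no setting showed a loss.

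The simulation error of a single power estimate from 1,500 trials is at most √(0.25/1500) = 1.3 points.

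**Other assumed rates.** With 95% symptom-free if absent and 55% versus 40% if present, simulated power went from 79% to 84% at q = 0.8 and from 60% to 71% at q = 0.6. These runs had only 150 trials each and are noisier. They show the same direction, and that the gain depends on the rates chosen.

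**Symptomatic attacks only.** Under the same 95/55/40 rates, a two-proportion approximation treating attacks as independent gives, at q = 0.6:
- all 240 attacks per treatment (71% versus 62%): power 55%;
- the 240 × 0.6 = 144 symptomatic attacks per treatment (55% versus 40%): power 72%.

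**Low-dose group.** Here "Approximately 48 subjects will be randomized in the low dose level", which is 96 attacks. At q = 0.75, about 24 attacks lack the symptom. The chance that all 24 stay symptom-free is about 0.92²⁴ = 14%, ignoring clustering within child. In that case the new covariate would separate.

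**The case against.** The strongest defence is that absence of the symptom across all treated attacks is a coherent endpoint and that nothing in the SAP contradicts it. Treatment order is randomised 1:1 (Section 2.3), so predose symptom status is independent of treatment in expectation. A chance difference between the ZNS and placebo attacks is ordinary sampling error, already reflected in the confidence interval. This stands: a reader might infer bias or a false-positive risk, and the SAP supports neither.

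A reader might also take a rise in the odds ratio after adjustment as the measure of what was lost. One simulation on the 92/55/42 rates, without predose pain in the model, moved the mean log odds ratio from 0.26–0.36 to 0.33–0.43. Part of that is non-collapsibility: adjusting a logit model for a predictive covariate moves the odds ratio away from 1 even under perfect balance. With symptoms very stable within child (latent correlation 0.95), the log odds ratio still rose from 0.27 to 0.35 at 40% prevalence while power rose by only 3 points. Nor does the covariate remove the dilution. The log odds ratio in symptomatic attacks is ln[(0.55/0.45)/(0.42/0.58)] = 0.52, above any adjusted value.

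It may also be tempting to call predose status the strongest predictor, or to say that it varies from attack to attack. The SAP says neither. Recording symptoms for a typical migraine (Section 4.3) suggests some stability within child, which reduces the gain.

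Finally, a model that is only similar to the primary one leaves slight room for a symptom baseline. The SAP never says so, however, and that choice is better fixed before unblinding. The points about small numbers in the low-dose group and missing predose entries also stand, and the change below deals with them.

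**Conclusion.** The point holds as a modest efficiency and presentation gap in three secondary endpoints. It does not touch the primary analysis, bias the estimates or inflate type I error. Under the 92/55/42 assumptions with 240 pairs, omitting the covariate costs about 1 to 7 points of power: least when the symptom is nearly constant within child, most when it varies between attacks. The all-attack difference is q times that in symptomatic attacks, provided attacks without the symptom at dosing respond alike on both treatments. The SAP gives neither the prevalence nor the response rates, so these sizes are illustrative. The direction is not in doubt if the symptom is absent at dosing in some attacks and its predose status predicts the outcome.

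**What to change.** In Section 5.3, with a note to the code in Section 8.1, state that for photophobia, phonophobia and nausea:

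1. the GEE includes predose presence (yes/no) of the same symptom in that period, alongside predose pain;
2. the proportions are also shown by treatment among attacks with the symptom present at dosing, because the covariate does not change the raw proportions;
3. a missing predose symptom entry is handled by a stated rule. Rules 1 and 2 of Section 2.5.1.1 are written for pain intensity, and carrying forward cannot fill a predose value;
4. in the low-dose group, the symptom covariate is dropped if the model separates or does not converge.

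The cost is a few sentences, one covariate already in the diary and one extra set of proportions. No new data are needed, and the primary analysis and study conduct are unchanged. It should be settled before the Part 1 unblinding.
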